## Glossary of terms

Control drug	Drugs(s) used as a comparator to reduce assessment bias, preserve blinding of investigational drug, assess internal study validity, and/or evaluate comparative effects of the investigational drug
Dosage	Dose of the study treatment given to the patient in a time unit (e.g. 100 mg once a day, 75 mg twice a day)
Enrollment	Point/time of patient entry into the study at which informed consent must be obtained (e.g. prior to starting any of the procedures described in the protocol)
Epoch	A portion of the study which serves a specific purpose. Typical epochs are: screening/recruitment, wash-out, treatment, and follow-up
Investigational drug	The drug whose properties are being tested in the study; this definition is consistent with US CFR 21 Section 312.3 and is synonymous with "investigational new drug" or "investigational medicinal product."
Medication pack number	A unique identifier on the label of each investigational drug package
Part	A single component of a study which contains different objectives or populations within that single study. Common parts within a study are: a single dose part and a multiple dose part, or a part in patients/subjects with established disease and in those with newly-diagnosed disease.
Patient/subject ID	A unique number assigned to each patient upon signing the informed consent
Randomization number	A unique identifier assigned to each randomized patient, corresponding to a specific treatment arm assignment
Study drug/ treatment	Any single drug or combination of drugs administered to the patient as part of the required study procedures; includes investigational drug (s), placebo/comparator active drug run-ins or background therapy
Study Treatment Discontinuation (TD)	When the patient permanently stops taking study treatment prior to the defined study treatment completion date
Variable	A measured value or assessed response that is determined in specific assessments and used in data analysis to evaluate the drug being tested in the study
Withdrawal of consent (WoC)	Withdrawal of consent from the study is defined as when a patient does not want to participate in the study any longer, and does not want any further visits or assessments, and does not want any further study related contact, and does not allow analysis of already obtained biologic material

## Amendment 2

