Older adults who are cognitively normal but who show elevated levels of amyloid at their initial assessment have an increased rate of progression to clinically classified MCI or dementia over 36 months, when compared to those with low levels of amyloid. This rate of clinical disease stage progression is increased dramatically if individuals with high levels of amyloid also meet clinical criteria for MCI at their initial assessment. In addition, data from previous studies in heart failure suggest that more than a third of patients are no longer on study medication by 3 years (I-Preserve study; Massie et al 2008). Thus the 3 year duration is considered to provide an appropriate time period to study the trial objectives while retaining as many evaluable patients as possible.

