### 5.6.2 Discontinuation of study treatment

Discontinuation of study treatment occurs when study drug is stopped earlier than the protocol planned duration, and this can be initiated by either the patient or the investigator.

The investigator must discontinue study treatment for a given patient if he/she believes that continuation would negatively impact the risk/benefit of trial participation.

Study treatment must be discontinued under the following circumstances:

- Patient wish
- Pregnancy (see [Section 6.5.9](#) and [Section 7.7](#))
- Use of prohibited treatment as per recommendation in [Table 5-3](#)
- Any situation in which study participation might result in a safety risk to the patient

However; study treatment discontinuation does not constitute withdrawal from the study and should not lead to the patient being withdrawn from the study.

Every effort should be made to complete end of treatment (EOT) assessments within 3 months of the last study drug dose for patients who have discontinued study drug permanently. For patients who terminate the study early, they are expected, and should be encouraged, to attend all the protocol specified study visits and perform all measurements as stipulated in the visit schedule ([Table 6-1](#)) and remain in follow up for the duration of the trial.

If they fail to return for these assessments for unknown reasons, every effort should be made to contact them. If the patient cannot or is unwilling to attend any visit(s), the site staff should maintain regular telephone contact with the patient, or with a person pre-designated by the patient. This telephone contact should preferably be done according to the study visit schedule.

The investigator must contact the IRT to register the patient's discontinuation from study treatment and must determine the primary reason for the patient's premature discontinuation of study treatment and record this information on the Dosage Administration eCRF.

The emergence of the following circumstances will require permanent study drug discontinuation:

- Withdrawal of informed consent
- Investigator thinks that continuation would be detrimental to the patient's well-being
- Suspected occurrence of angioedema. A patient with any signs or symptoms of clinically significant angioedema should be thoroughly evaluated by the investigator

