Apart from the above analyses, dose administration records for double-blind period will also be listed at a patient level for the patients in safety set with reasons for changing dose.

Number and percentage of patients with treatment interruption and permanent treatment discontinuations will be provided by reason for treatment interruption or discontinuation. Time from randomization to permanent study treatment discontinuation will be summarized by treatment group by providing Kaplan-Meier estimate of cumulative rate of permanent treatment discontinuation.

Compliance with respect to protocol specified study treatment will be summarized based on the site reported compliance for by actually received treatment group and overall during randomized treatment epoch for all patients in Safety set (SAF)

All these analyses pertaining to treatment exposure during double-blind period will be carried out for all patients in Safety set (SAF). Compliance summary will also be provided for patients in Full Analysis set (FAS).

Summaries of duration of treatment exposure in the double-blind phase will also be provided separately for subjects included in the PET imaging substudy.

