1. Multiple (e.g. 100) imputations of missing GCCS values under a MAR assumption are generated, resulting in multiple (100) complete data sets. This imputation is based on predicted GCCS values from the fitted repeated measures ANCOVA model for the GCCS values (at baseline, Weeks 26, 52, 78, 104, 130 and Week 156) with treatment, age group (<75, ≥75 years), baseline MMSE status (<28, ≥28), baseline cerebrovascular disease burden, visit and treatment-by-visit interaction as factors having fixed effects assuming a common unstructured covariance matrix among visits between treatment group. SAS proc MI FCS statement is used to impute missing values in the following sequence: factor variables in the increasing order of missing frequency, the GCCS at baseline, Weeks 26, 52, 78, 104, 130 and Week 156.
2. For each completed data set, the imputed GCCS values at a given visit for patients who died, or had a HF hospitalization or stroke since the preceding visit, a penalty factor would be applied to the imputed values to reflect that the MAR approach may have overestimated the missing values, e.g. by assuming the actual GCCS values could be a certain percentage (e.g. 5%) worse than MAR based imputations for discontinuations due to death, HF hospitalization and stroke. If the MAR-imputed GCCS value is positive, the final value will be 95% x the imputed value; if the MAR-imputed GCCS value is negative, the final value will be 105% x the imputed value.
3. The primary analysis model as described above will be fitted to the 100 completed data sets following the application of the penalty factor in step 2 which produces 100 sets of parameter estimates and associated covariance matrices.
4. These 100 sets of parameter estimates are then combined by using Rubin's rules to derive overall estimates and their confidence intervals. In a similar manner to the primary analysis, a standardized effect size estimate (Cohen's d) and 95% CI will also be reported using the pooled SD.

The analysis will be repeated for varying penalty factors in a range between 0 and 50%. It is performed using 'on-treatment' data in the SAF, as done in the primary analysis. Tipping point analyses will be performed separately to assess the sensitivity of the results to MAR assumptions under the following situations:

- for missing data due to censoring at the start of AD and cognitive impairment treatments, including on-treatment data only in the SAF

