$X_i(t)$ = Covariate vector having fixed effects on mean GCCS outcome for i-th patient (treatment, age stratification factor, MMSE stratification factor, education level, baseline

cerebrovascular disease burden, APOE4 status, baseline GCCS, assessment time, assessment time by baseline GCCS and assessment time by treatment)

β = Parameter vector representing fixed effects of covariate vector $X_i(t)$ on mean GCCS outcome at time t

b_{0i} =Patient-specific random intercept

b_{1i} =Patient-specific random slope on time

$e_i(t)$ = Measurement error,

Assumption:

- (b_{0i}, b_{1i}) 's are assumed to be following bivariate normal distribution with mean vector 0 and unstructured covariance matrix independently for all patients
- $e_i(t)$'s are assumed to be independently normally distributed with mean vector 0 and an covariance matrix with no correlation between the time points and an common variance σ_e^2 on the diagonal elements

Model for time to starting AD or CI related medication

Time to starting AD or CI related medication from randomization will be calculated as –

- Date of starting AD or CI related medication – Randomization date +1

Patients who do not start AD or CI related medication, their data will be censored at the earlier of –

- Last known date patient took study medication
- Date of withdrawal of consent
- Date of last visit

A exponential regression is fitted to the time to starting AD or CI related medication.

$$\lambda_i(t|H_i(t), X_i) = \lambda_0 \exp(X_i^T \gamma + \alpha m_i(t))$$

where

$\lambda_i(t|H_i(t), X_i)$ =Conditional intensity function at time t for i-th patient given the covariate and history of outcomes until time t, $H_i(t)$

λ_0 =Baseline hazard function that is constant over time

γ = Parameter vector representing fixed effects of time-independent covariate vector X_i on event risk (hazard) at time t

α =Fixed effect of ‘true’ patient-specific mean outcome at time t

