3.3 Blinded sample size re-estimation

Approximately 520 patients will be randomized in order to provide overage to account for the information loss caused by an estimated 30% "drop-out" (including death, lost-to-follow-up, permanent discontinuation of study medication and start of treatments for AD or cognitive impairment) during 3 year period. In the PET imaging substudy approximately 430 patients will be randomized.

A loss of 30% of information is a crude estimate therefore it is planned to monitor the 'dropout' pattern as the trial is ongoing in order to provide a better prediction of the information loss for a given number of patients. The final number of patients randomized may be reduced if there is sufficient evidence that the information loss will be less than 30% and that the precision of the estimates of treatment effect (as described in the sample size section above), will be maintained.

4 Change to protocol specified analyses

Not applicable

5 Appendix

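### The Kaplan-Meier summary of permanent study-drug discontinuation has no rule for death on drug; cumulative incidence with death as a competing event would settle its meaning

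*SAP*

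**What the plan says.** In SAP 2.4.1, under treatment exposure during the double-blind epoch, time from randomization to permanent discontinuation is to be summarised by treatment group, "providing Kaplan-Meier estimate of cumulative rate of permanent treatment discontinuation". The set is the Safety set. No event definition, censoring rule or competing-event rule accompanies it. The sentence before it plans a crude tabulation: "Number and percentage of patients with treatment interruption and permanent treatment discontinuations will be provided by reason for treatment interruption or discontinuation".

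Elsewhere the documents define or describe discontinuation in ways that differ on death:

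- The protocol glossary is broad: "When the patient permanently stops taking study treatment prior to the defined study treatment completion date".
- SAP 2.5.5, on the tipping-point analysis, refers to "MAR based imputations for discontinuations due to death, HF hospitalization and stroke", so there death is a reason for discontinuation.
- Protocol 5.6.2 is narrower. It describes study drug stopped before the planned duration, and says that "this can be initiated by either the patient or the investigator".
- SAP 3.3 counts death and drug discontinuation as separate components of drop-out: "including death, lost-to-follow-up, permanent discontinuation of study medication and start of treatments for AD or cognitive impairment".

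The one written time-to-event censoring rule in the visible SAP concerns a different endpoint, the start of medication for Alzheimer's disease or cognitive impairment (SAP 2.5.5): "Patients who do not start AD or CI related medication, their data will be censored at the earlier of" last study medication, consent withdrawal and last visit.

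**The concern.** A patient who dies while taking study drug can no longer discontinue it. If such a patient is censored, Kaplan-Meier treats the patient as still able to stop later. 1-KM then estimates the proportion who would stop if nobody died, which is not the proportion who did stop. If death is instead an event, the curve no longer describes discontinuation alone.

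So one SAP sentence supports two quite different curves, and two programmers could each comply and produce different ones. The curve describes how long patients stayed on drug in each arm, which is background to the on-treatment analyses of GCCS and SUVr. SAP 2.5.5 itself raises the possibility of lower mortality on LCZ696, so the handling of death could also affect how the arms compare on this display.

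**Working it through.** The plan states no expected discontinuation or death rate for this summary, so there is no figure to reproduce.

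**Inputs**

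- Total loss over 3 years: 30% (SAP 3.3). I treat all of it as discontinuation or death on drug. That is a simplification, because the 30% also includes loss to follow-up and starts of AD treatment.
- Variant: 34%, for the statement in Protocol 3.2 that in an earlier heart-failure trial "more than a third of patients are no longer on study medication by 3 years".
- Deaths on drug: not given. Assumed 5%, 10% and 15% (3% to 15% in the variant).
- Patients per arm: 520/2 = 260.

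**Formulas** (constant hazards, T = total exit, p = share of exits that are deaths)

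- Actual proportion discontinuing (cumulative incidence) = T(1-p)
- 1-KM with death censored = 1-(1-T)^(1-p)
- 1-KM with death as an event = T

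**Results at T = 30%**

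| Deaths on drug | p | Actually discontinued | 1-KM, death censored | Excess (points) | 1-KM, death an event |
|---|---|---|---|---|---|
| 5% | 1/6 | 25.0% | 1-0.70^(5/6) = 25.7% | +0.7 | 30.0% |
| 10% | 1/3 | 20.0% | 1-0.70^(2/3) = 21.2% | +1.2 | 30.0% |
| 15% | 1/2 | 15.0% | 1-0.70^(1/2) = 16.3% | +1.3 | 30.0% |

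A simulation of the 10% row (260 per arm, 4,000 runs) gives 21.2% for 1-KM and 20.0% for the crude proportion. The standard error of the crude proportion is sqrt(0.20 x 0.80/260) = 2.5 points. At T = 34%, the excess runs from +0.5 (3% deaths) to +1.7 points (15% deaths).

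**Between arms, with death censored**

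- Same discontinuation hazard in both arms (1-KM = 25%): with 8% deaths the actual proportion is 23.9%, an excess of 1.1 points. With 10% deaths it is 23.6%, an excess of 1.4. The excesses differ by 0.3 points.
- Same actual proportion, 25% in each arm, with deaths of 8% and 14%: 1-KM is 1-0.67^(25/33) = 26.2% and 1-0.61^(25/39) = 27.2%.
- Different discontinuation: 10% stopping and 12% dying gives an excess of 0.7 points, while 25% stopping and 8% dying gives 1.2. Here the arm with more deaths has the smaller excess.

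**Spread from the missing rule.** At 20% stopping and 10% dying, the same sentence yields 21.2% (death censored) or 30.0% (death an event), against 20.0% actually discontinuing.

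**The case against.** The strongest reply is that nothing in the SAP says death is censored. The glossary wording and the tipping-point text can both be read as counting death as a discontinuation, and on that reading the upward error disappears. This stands, so the censoring problem is conditional. It does not rescue the sentence, because the curve then mixes death with discontinuation under a label that names only the latter.

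The second reply is that the actual percentage is already planned. Crude numbers by reason come in the preceding sentence. With fixed 3-year follow-up and little other censoring, they will be close to the cumulative incidence. Deaths by arm (SAP 2.7.3), disposition with reasons (SAP 2.3.1) and exposure-duration categories (SAP 2.4.1) are planned too. The by-visit summaries of GCCS and SUVr show directly how much data remain. This also stands and limits the harm. What is left is a curve that, if death is censored, will disagree with the crude percentage beside it without explanation.

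The third reply is size: an excess of about 1 point, against a standard error of about 2.5 points per arm. In addition, the 26.2% versus 27.2% contrast is not purely an artefact. Equal actual proportions with unequal deaths imply a higher discontinuation hazard in the arm with more deaths, and Kaplan-Meier reflects that. Both points are correct.

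**Conclusion.** The point holds as a gap in definition with a small effect. The summary lacks a rule for death on drug, and Kaplan-Meier is the weaker choice on either reading: it overstates the proportion stopping if death is censored, and it merges two outcomes if death is an event. The overstatement rests on constant hazards, on assigning the full 30% loss to discontinuation or death, and on assumed death percentages. If part of the 30% is other loss, the excess is smaller at a given death percentage.

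Three stronger readings are tempting and are not supported:

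- A reader might infer that the plan censors deaths and that its reported discontinuation percentage is therefore too high. The censoring is an inference, and the crude percentage is reported as well.
- A reader might infer that the error is always larger in the arm with more deaths. That needs similar discontinuation in both arms, as the last between-arm example shows.
- A reader might take the one-third figure as discontinuation excluding deaths and add 8% to 15% deaths, which gives an excess of 1.6 to 3.3 points. That figure describes an earlier trial and its wording does not exclude deaths. The sum also implies a total exit of about 41% to 48%, against the plan's 30%.

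The curve enters no model or test, so neither the primary GCCS result nor the SUVr result changes.

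**What to change.** In SAP 2.4.1, replace the Kaplan-Meier estimate with the by-arm cumulative incidence (Aalen-Johansen) of permanent study-drug discontinuation, with death on drug as a competing event. State that only patients who complete treatment to the end of study, and those whose drug status is unknown, are censored. Show the cumulative incidence of death on drug beside it, so that (with no earlier censoring) discontinued, died on drug and still on drug add to 100% in each arm.

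The cost is a sentence or two in the SAP and a standard option in the software already planned (SAS PROC LIFETEST with EVENTCODE). No new data are needed. If deaths would otherwise have been censored, the reported figure falls slightly. If they would have been counted as events, it falls by the proportion dying on drug, which then appears on its own curve.

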2.4.2 Prior, concomitant and post therapies

Medications will be identified using Novartis Drug and Therapy Dictionary, NovDTD which is a modified Novartis internal version WHO Drug Dictionary Enhanced (DDE) including Anatomical Therapeutic Chemical (ATC) code. The latest version at the time of database lock will be used.

For the run-in phase, the run-in concomitant medication information will be summarized based on the ENR.

Prior and run-in concomitant medications taken at any time between the screening visit and the randomization visit will be summarized in sequential format by treatment of valsartan for the VRS and LCZ696 for the LRS based on the latest version of the dictionary. Medications will be presented in alphabetical order, by ATC codes and grouped by *anatomical main group* (the 1st level of the ATC codes). Tables will show the overall number and percentage of patients receiving at least one drug of a particular ATC code and at least one drug in a particular anatomical main group.

Prior medications are defined as drugs taken prior to first dose of run-in study medication. Any medication given at least once between the day of first dose of run-in study medication and the last day prior to randomization visit will be a **run-in concomitant medication**, including those which were started pre-screening and continued into the run-in phase. Prior or run-in concomitant medication will be identified based on recorded or imputed start and end dates of taking medication. The rules for imputing incomplete (start and end) dates are described in [Section 5](#).

The concomitant medication information for the double blind phase will be summarized based on the SAF.

Concomitant medications taken at any time since the randomization visit will be summarized by treatment group based on the latest version of the dictionary. As before, medications will be presented in alphabetical order, by ATC codes and grouped by anatomical main group (the 1st level of the ATC codes). Tables will also show the overall number and percentage of subjects receiving at least one drug of a particular ATC code and at least one drug in a particular anatomical main group.

Any medication given at least once between the day of first dose of randomized study medication and the last day of study visit will be a double-blind concomitant medication, including those which were started pre-randomization visit and continued into the double blind treatment phase.

Heart Failure and CV medications

The following important classes of concomitant heart failure and CV medications administered during run-in and during double blind phase will be summarized separately in a similar way as described above.

- ARBs
- ACE inhibitors
- Renin inhibitors
- Diuretics
- Beta blockers
- Aldosterone antagonists
- Cardiac glycosides (Digoxin/digitalis glycoside)
- Calcium antagonists
- Other vasodilators
- Oral anticoagulants
- Antiarrhythmic agents
- Aspirin
- Other antiplatelet agents
- Statins
- Nitrates
- Other lipid lowering agents
- SGLT2

Medications for treating AD or cognitive impairment

Concomitant use of AD or cognitive impairment related medication will be summarized by treatment group separately for patients newly starting such medications during post-randomization phase. Treatments for AD or cognitive impairment include:

- Glutamate receptor antagonists (memantine)
- Cholinesterase inhibitors (donepezil, galantamine, and rivastigmine).

The classes of medications criteria searching the heart failure, CV medications and AD or cognitive impairment medications will be defined in a separate EXCEL sheet with ATC preferred term and WHO drug code. This EXCEL sheet will be stored in CREDI at the RAP level after the content is agreed to by the Global Program Medical Director (GPMD) and prior to CDBL

